3.7.1.1. Treatment Compliance

Study drug compliance will be calculated as:

$$\frac{100 \times 0.5 \times (\text{number of capsules dispensed} - \text{number of capsules returned})}{(\text{date of last dose} - \text{date of first dose} + 1)}$$

Study drug compliance over the interval from first to last dose in the induction period and the study overall will be summarized as a continuous variable and by rounding to the nearest 0.1% and showing counts and percentages for the following disjoint categories:

- $\geq 120\%$;
- 110% to 120%;
- 90% to 110%;
- 80% to 90%;
- $< 80\%$;

Study drug administration information (date/time and study day) will be provided in a data listing. Study drug accountability information and study drug exposure and compliance will also be provided in data listings.

Study drug discontinuations and reasons for study drug discontinuation will be listed.

3.7.2. Adverse Events

Adverse events (AEs) will be coded to the preferred terms (PT) of the Medical Dictionary for Regulatory Activities (MedDRA®). Summaries for induction period and for the complete study period will be presented separately and by system organ class (SOC), preferred term, and severity and/or relatedness, the number and percentage of subjects for whom events were reported.

Adverse events (AEs) are recorded from signing of the informed consent form through the final follow-up assessment. Adverse events observed prior to first dose are non-treatment emergent.

All summaries will be presented for both the Induction Period and the overall study period separately.

Treatment emergent adverse events are defined as follows for induction period and overall:

- Induction period TEAEs are events with a start date/time after the first dose date/time in Induction period up to the date/time of ATE Day 1 dose or date of last dose of study drug + 28 days, whichever is earlier.
- TEAEs for the whole study and listings are defined as AEs with onset on or after the first initiation of study drug up to the date of last dose study drug + 28 days.

Only treatment-emergent AEs will be summarized in the tables. Separate by-subject listings of all TEAEs and all non-TEAEs will be provided.

An AE will be considered a treatment-emergent serious AE (TESAE) if it is a TEAE that additionally meets any SAE criteria.

If more than 1 AE is coded to the same preferred term for the same subject, the subject will be counted only once for that preferred term using the most severe and most related occurrence for the summarizations by severity and by relationship to study drug.

Summary tables will also be provided for Induction period and overall for subjects with:

- TESAEs by SOC and PT
- TEAEs leading to discontinuation of study drug by SOC and PT
- Drug related TEAEs by SOC and PT
- TEAEs by severity and by SOC and PT
- TEAEs resulting in death by PT

Listings of all AEs, SAEs, and AEs leading to premature study drug discontinuation by subject will be presented.

An overall summary of adverse events will also be presented and will include the following summary lines: Any AE, Moderate or Severe AEs, AEs Related to Study Drug, Moderate or Severe AEs Related to Study Drug, Serious AEs, Serious AEs Related to Study Drug, AEs Leading to Premature Study Drug Discontinuation, AEs Leading to Temporary Interruption of Study Drug, and Deaths During Study.

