6.4.3. Medical History

A medical history will be taken during Screening and will include evaluation for past and present cardiovascular, respiratory, GI, renal, hepatic, neurological, endocrine, lymphatic, hematologic, immunologic, dermatologic, psychiatric, genitourinary diseases, surgical history, or any other diseases or disorders. An updated medical history will be obtained on Day 1 prior to dosing. Medical events or conditions that arise or worsen in severity or frequency following informed consent will be recorded as an AE; those after initiation of study drug will be recorded as a treatment-emergent AE.

Regarding the subject's history of CD, diagnosis date, extent of disease (categorized as ileal, colonic, ileocolonic), presence of complications (fistula [including number, location, and drainage status], abscess [including location], oral manifestations, arthralgia), documented in the appropriate eCRF. The number of stools per day (rounded to the nearest whole digit) when the subject was feeling normal (without a flare or before the diagnosis of CD) will be recorded in the eCRF.

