7.1.1. Adverse Events (AE)

An AE is any untoward medical occurrence in a patient or clinical trial subject administered a pharmaceutical product that does not necessarily have to have a causal relationship with this treatment. An AE can therefore be any unfavorable and unintended sign (including an abnormal laboratory finding), symptom, or disease temporally associated with the use of a medicinal product, whether or not related to the medicinal product.

- AEs may be new events
- Preexisting events that increase in frequency, severity or change in nature or seriousness during or as a consequence of participation in clinical studies.
- Pre- or post-treatment complications that occur as a result of a protocol-mandated procedure (such as a biopsy).
- AEs may be clinically significant changes from baseline in physical examination, laboratory tests, or other diagnostic investigation (e.g., laboratory results, x-ray findings).
- AEs may result from an overdose of the study medication.

Whenever possible, the diagnosis (rather than a series of terms related to a diagnosis) should be recorded as the AE term.

An AE does not include the following:

- Medical or surgical procedures (such as surgery, endoscopy, tooth extraction, or transfusion); the condition that leads to the procedure is an adverse event
- Preexisting diseases or conditions present or detected before signing an informed consent form that do not worsen
- Situations where an untoward medical occurrence has not occurred (such as hospitalization for elective surgery or social and/or convenience admissions)
- Overdose of either study drug or concomitant medication without any signs or symptoms, unless the subject is hospitalized for observation

Any medical condition or clinically significant laboratory abnormality with an onset date prior to the time the subject signed the informed consent form is considered to be preexisting and should be documented in the medical history CRF.

Pregnancy is not an AE; however, if a female subject becomes pregnant during the study from the time of consent until 7 days after the subject’s last dose of study drug, Theravance Biopharma, Inc. (TBPH) will be notified according to the procedures for SAE reporting as

outlined in Section 7.4.3. Follow-up information regarding the outcome of the pregnancy and any fetal or neonatal sequelae will be obtained and documented.

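### The onset-only TEAE rule in SAP 3.7.2 leaves open how a screening adverse event that worsens or becomes serious on study drug is counted, and it does not match Protocol 6.4.3

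*SAP*

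**What the plan says.** SAP 3.7.2 collects adverse events from informed consent onward and gives two definitions, both resting on when the event began. For Induction: "Induction period TEAEs are events with a start date/time after the first dose date/time in Induction period", closing at the ATE Day 1 dose or 28 days after the last dose, whichever comes first. For the whole study: "AEs with onset on or after the first initiation of study drug up to the date of last dose study drug + 28 days". Neither has a limb for worsening. The section also states "Adverse events observed prior to first dose are non-treatment emergent", without qualification.

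Two further sentences carry that rule into the outputs. The first is "Only treatment-emergent AEs will be summarized in the tables". The second is "An AE will be considered a treatment-emergent serious AE (TESAE) if it is a TEAE that additionally meets any SAE criteria". Non-TEAEs are listed by subject, as are all AEs and all SAEs.

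The protocol speaks on this in three places:

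- Section 6.4.3 covers conditions that first appear, or get worse in severity or frequency, after consent. These are AEs, and "those after initiation of study drug will be recorded as a treatment-emergent AE".
- Section 7.1.1 includes in its AE definition "Preexisting events that increase in frequency, severity or change in nature or seriousness" during, or as a result of, taking part in the study.
- Section 8.8.2, the analysis section, defines a TEAE as one that begins on or after first dose, introduced as a general rule. It leaves the assignment of TEAEs to study phases to the SAPs.

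**The concern.** Screening can last up to 35 days, so some subjects will start study drug with an adverse event already on record. Take one that was mild in screening and becomes severe, or leads to hospital admission, on treatment. Protocol 6.4.3 treats the worsening as treatment-emergent. The SAP looks only at when the event began.

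If the event keeps its screening onset, it fails the TEAE test. It then leaves several tables at once: overall TEAEs, TEAEs by severity, drug-related TEAEs, TEAEs leading to discontinuation, and TESAEs. Safety and tolerability is one of the two primary objectives, and the placebo arm has about 40 subjects, so a single serious event can change how a table reads. A summary meant to show what happened on drug should not depend on how each site happened to enter a worsening.

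**Working it through.** The plan gives no figure to reproduce, and the point rests on no sample size, power or event count. The check sets the rules side by side and follows an event through them.

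| Source | Purpose | Test for treatment-emergent | Worsening covered? |
|---|---|---|---|
| Protocol 6.4.3 | Recording of history and AEs | Arises or worsens after study drug starts | Yes: severity or frequency |
| Protocol 7.1.1 | Definition of an AE | Not addressed | Yes, as an AE: also nature and seriousness |
| Protocol 8.8.2 | Analysis definition | Begins on or after first dose | No |
| SAP 3.7.2 | Analysis definition | Start or onset relative to first dose | No |

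The protocol therefore differs within itself (6.4.3 against 8.8.2), and the SAP takes the 8.8.2 side.

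*Which events are exposed.* A condition that predates consent belongs to medical history. If it worsens on drug, it first becomes an AE at that point, its onset falls after first dose, and it is a TEAE under every definition. The exposed group is narrower: events first recorded as AEs between consent and first dose, still present at first dose, that then worsen.

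*Path A: the worsening is entered as its own AE, dated when it occurred.* The start is after first dose, so the event is a TEAE, and a TESAE if serious. It enters the tables and nothing is lost.

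*Path B: the screening record stays open and its severity or seriousness is updated.* The onset is before first dose, so the event is not a TEAE. A TESAE qualifies only "if it is a TEAE that additionally meets any SAE criteria", so it is not a TESAE either. It appears in the listings alone.

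*Which path applies.* Protocol 7.3 names the fields collected for an AE, among them onset, resolution and severity. Section 7.4.2 gives recording rules, and 7.5 requires follow-up to resolution or a stable endpoint. None says whether a change in severity closes one record and opens another. Sections 6.4.3 and 7.1.1 lean towards Path A. The CRF completion instructions, which might settle it, are not among the documents.

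*The ATE boundary.* Subjects on placebo in Induction move to 80 mg at ATE Day 1. Under a single record, an AE that began on placebo is an Induction TEAE by its start date. If it becomes severe or serious on 80 mg, the record carries the later grade. SAP 3.7.2 does not say which grade the Induction table should show, so on-drug severity could appear in the placebo column.

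**The case against.** The strongest reply is that the SAP nowhere says a pre-dose event stays non-treatment-emergent after it worsens. A worsening seen on drug is not plainly an event observed before first dose. Protocol 6.4.3 is a recording instruction, and read with 7.1.1 it points to a fresh AE dated on drug, which the SAP would tabulate. The SAP also follows the protocol's own analysis definition in 8.8.2. All of this stands. It makes the loss conditional, but it does not tell a programmer or a site what to do.

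A reader might infer that serious on-drug events are certain to leave the safety tables. The documents do not support that, because Path A is open and is arguably the better reading. Nor is this simply the SAP against the protocol, since 8.8.2 has the same gap.

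A reader might also infer that such events appear in no comparison with placebo. That does not hold for laboratory findings. SAP 3.7.3.1 summarizes changes from baseline, shifts against normal ranges and maximum post-baseline CTCAE grade, whatever the AE status, and SAP 3.1 presents summaries by treatment. Those summaries do not cover clinical events such as infections.

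Eligibility narrows the pool further. Exclusion 503 bars most active, clinically significant infections within 30 days before Day 1, and exclusion 602 bars clinically significant laboratory abnormalities at screening. Milder events can still enter.

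On the ATE, SAP 3.7.2 plans Induction and overall summaries but no ATE-only AE table. A placebo-period event that worsens on 80 mg is already an overall TEAE. What remains there is only the severity and seriousness shown in the Induction table.

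**Conclusion.** The gap is real and conditional. SAP 3.7.2 and Protocol 8.8.2 define TEAEs by onset and do not carry over the worsening limb of Protocol 6.4.3, and no visible passage says how a worsened screening event is recorded. If it stays on one record with its pre-dose onset, it is missing from the TEAE and TESAE summary tables and survives only in listings. If a new record is opened, there is no loss.

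No size can be derived. One might compare the length of screening with the 12 weeks of Induction to get a share of affected events. That would count events resolved before Day 1, which cannot worsen on drug, and it would need a worsening rate that the documents do not give. The number is probably small. The case for acting is that the affected events are, by construction, those that worsened on treatment, and that the repair is cheap.

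**What to change.** Reconcile SAP 3.7.2 and Protocol 8.8.2 with Protocol 6.4.3. In SAP 3.7.2, replace the sentence on events observed before first dose with: *An AE with onset before first dose that increases in severity or frequency, or becomes serious, on or after first dose is a TEAE dated to the worsening.* The existing end-of-window limits would then apply to the date of worsening. Put the same rule in Protocol 8.8.2.

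Add a second sentence: an Induction AE that worsens after ATE Day 1 is shown in the Induction tables at the severity and seriousness it had during Induction.

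The cost is SAP and protocol wording, plus a limited query for worsening dates among AEs ongoing at first dose and at ATE Day 1, best completed before the relevant database lock. TEAE counts may rise slightly. If sites already open a new record on worsening, the first rule changes no table and simply documents the practice.

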8.8. Safety Analyses

Safety data will be summarized by treatment received; specifically, induction safety data will be summarized by treatment received during induction and ATE safety data by treatment received during the ATE. Summaries will be provided by nominal visit and time point or for the entire treatment period, as appropriate for the type of data. Quantitative data collected at unscheduled times will be listed but will not be included in summaries. Categorical data collected at unscheduled times (e.g., ECG finding categories) will not be included in summaries by time point but will be included in summaries of findings during the entire treatment period.

[REDACTED]

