8.8.2. Adverse Events

AEs will be coded to the preferred terms of the Medical Dictionary for Regulatory Activities (MedDRA®). Summaries will present by system organ class (SOC), preferred term (PT), and severity (mild, moderate, severe) the number and percentage of subjects for whom events were reported.

In general, a treatment-emergent adverse event (TEAE) will be defined as any AE that begins on or after the date and time of the first dose of study drug and up to the date of last dose of study drug plus the number of days in the follow-up period.

TEAEs will be summarized separately for the Induction and ATE phases. Assignment of TEAEs to different phases of the study (Induction or ATE) will be detailed in the SAPs.

All AEs will be listed by subject. The number and percentage of subjects who experience TEAEs will be summarized. Summaries of TEAEs will include the following types of summaries:

- All AEs, by SOC and PT and also by PT (by descending overall frequency)
- All AEs, by SOC, PT, and severity
- All study drug-related AEs, by SOC and PT
- All study drug-related AEs, by SOC, PT, and severity
- All AEs leading to premature discontinuation of study drug, by SOC and PT
- All AEs leading to temporary interruption of study drug, by SOC and PT
- All SAEs, by SOC and PT
- All study drug-related SAEs, by SOC and PT

A listing will be provided for all subjects who experience an SAE. Listings will also be provided for subjects who discontinued study treatment prematurely because of AEs and subjects who temporarily interrupted study treatment because of AEs. AEs of Special Interest, as described in Section 7.1.4, will be listed and summarized.

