All subjects who complete Induction at the Week 12 visit will continue into ATE, ATE Day 1 is scheduled for between 1 and 7 days after the Induction Week 12 visit where subjects will be treated with either 80 mg or 200 mg of TD-1473 for 48 weeks. Dose during ATE depends on treatment assignment during Induction (Figure 1 and Table 2): those who were dosed with TD-1473 during Induction will stay on the same dose; those who were dosed with placebo during Induction will be dosed with TD-1473 at 80 mg.

Table 2: Induction and Active Treatment Dose Assignment

Induction Dose (3:3:2 randomization)	Active Treatment Extension (ATE) Dose
80 mg	80 mg
200 mg	200 mg
Placebo	80 mg

During ATE, subjects will undergo clinic study visits every 4-12 weeks. Subjects will continue to complete a daily diary.

Subjects who have not shown clinical improvement (as assessed by the investigator) 16 weeks after initiation of ATE (i.e., ATE Week 16) will be discontinued from the study following completion of an End of Study (EOS) visit.

End of Study (EOS) Visit:

An EOS visit will be required for all subjects 4 weeks following their last dose of study drug. Subjects who complete an Early Study Drug Discontinuation visit during Induction or ATE will also be required to return for an EOS visit.

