1.2.2. Definition of Study Drugs

Study drug comprises the following (placebo and 2 doses of TD-1473):

- TD-1473 80 mg once daily: Taken orally for up to 60 (including ATE) weeks in the morning before eating. Subject must refrain from eating or drinking anything other than water and non-study medications for at least 30 minutes after dosing. Subjects from placebo arm will take from start of ATE Day 1 to ATE week 48.
- TD-1473 200 mg once daily: Taken orally for up to 60 (including ATE) weeks in the morning before eating. Subject must refrain from eating or drinking anything other than water and non-study medications for at least 30 minutes after dosing.

Placebo once daily: Taken orally for up to 12 weeks in the morning before eating. Subject must refrain from eating or drinking anything other than water and non-study medications for at least 30 minutes after dosing.

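### Overall-study adverse event percentages span unequal exposure and the placebo-to-80 mg switch, with no readable ATE-only table; whether they exaggerate or dilute a drug effect depends on the column rule

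*SAP*

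**What the plan says.** SAP 3.7.2 tabulates adverse events as "the number and percentage of subjects for whom events were reported", by system organ class and preferred term. Of the periods covered it says: "All summaries will be presented for both the Induction Period and the overall study period separately". Induction TEAEs stop at the ATE Day 1 dose, or 28 days after last dose if sooner. Whole-study TEAEs are "AEs with onset on or after the first initiation of study drug up to the date of last dose study drug + 28 days".

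Exposure differs by treatment. SAP 1.2.2 gives "Placebo once daily: Taken orally for up to 12 weeks in the morning before eating"; each TD-1473 dose is "Taken orally for up to 60 (including ATE) weeks in the morning before eating". SAP 1.2.1 adds that "those who were dosed with placebo during Induction will be dosed with TD-1473 at 80 mg", while the active arms keep their dose.

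The protocol splits the data differently. Section 8.8.2 says "TEAEs will be summarized separately for the Induction and ATE phases", and 8.8 asks for "ATE safety data by treatment received during the ATE". The SAP defines an ATE period (3.1.5.2), but its readable text gives TEAE definitions only for Induction and the whole study. SAP 5.1, which records changes from the protocol, has no readable content.

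The sentence in SAP 3.7 introducing the overall exposure, compliance and adverse event summaries breaks off at a comma in the public copy. That may be lost or redacted text and is not treated here as a fault. Table 5 assigns the Safety set by actual treatment and points to 3.1.6, but that section deals with wrongly dispensed drug, not with the planned switch.

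**The concern.** A subject percentage has no time in its denominator. It compares groups fairly only if they were observed for similar lengths of time on the treatment named in the column. Induction meets that condition by design. The overall period does not: a placebo subject who completes Induction contributes up to 12 weeks on placebo and then up to 48 on 80 mg. ATE length also varies between subjects, because non-improvers stop at ATE Week 16 and the study was terminated early (SAP section 1).

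Safety and tolerability are a primary objective. Events first arising after Week 12 reach only the overall tables, and several adverse events of special interest, such as malignancy, thromboembolism and opportunistic infection, may well appear late. If the overall table cannot separate drug from time, or placebo time from 80 mg time, it says little about those events.

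**Working it through.** The documents give no figure for adverse event incidence, so there is none to reproduce. The stated 60-week maximum is confirmed: 12 weeks of Induction + 48 of ATE = 60.

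**Inputs from the documents.** Planned arms 40 placebo, 60 at 80 mg, 60 at 200 mg (SAP 1.3); exposure as above.

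**Assumptions.** Constant hazard, full completion, all placebo subjects entering the ATE, and a 12-week risk p of 10% (5% and 20% also shown). The 28-day tail is ignored. Risk over w weeks = 1 − (1 − p)^(w/12).

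**A. Columns by treatment received, no drug effect.** The 80 mg column holds 60 subjects at 60 weeks and 40 switchers at 48.
- Mean exposure at 80 mg: (60×60 + 40×48)/100 = 55.2 weeks. Ratios to placebo: 55.2/12 = 4.6 and 60/12 = 5.0. Ratio of 200 mg to 80 mg: 60/55.2 = 1.09.
- Placebo: 10.0%.
- 200 mg: 1 − 0.9^5 = 41.0%.
- 80 mg: 0.6 × (1 − 0.9^5) + 0.4 × (1 − 0.9^4) = 0.6 × 0.4095 + 0.4 × 0.3439 = 38.3%.

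| p in 12 weeks | ATE weeks reached | Placebo | 80 mg | 200 mg |
|---|---|---|---|---|
| 5% | 48 | 5.0% | 21.0% | 22.6% |
| 10% | 48 | 10.0% | 38.3% | 41.0% |
| 20% | 48 | 20.0% | 64.0% | 67.2% |
| 10% | 24 | 10.0% | 23.9% | 27.1% |
| 10% | 12 | 10.0% | 15.4% | 19.0% |

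**B. Columns by randomized sequence.** Planned follow-up is 60 weeks in each. With no drug effect all three show 41.0%, so there is no false gradient. Now let active drug have a hazard ratio of 2, with a 10% placebo risk:
- Induction: placebo 1 − 0.9 = 10.0%; active 1 − 0.9^2 = 19.0%; ratio 1.90.
- Overall: placebo then 80 mg 1 − 0.9^(1 + 2×4) = 1 − 0.9^9 = 61.3%; active throughout 1 − 0.9^10 = 65.1%; ratio 1.06.

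A person-time denominator alone does not repair B. The rate ratio by sequence would be (2×60)/(12 + 2×48) = 120/108 = 1.11. Time and events must also be split at the switch.

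**C. Rates by treatment being taken, no drug effect.** Planned person-years are 40×12/52.18 = 9.2 on placebo, 5,520/52.18 = 105.8 on 80 mg and 3,600/52.18 = 69.0 on 200 mg. The underlying rate is −ln(0.9)/12 × 52.18 × 100 = 45.8 per 100 person-years in every column. The gradient in A disappears.

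**The case against.** The strongest reply is that the harm cannot be asserted without the column rule. A reader might infer that overall differences reflect exposure time rather than drug whatever the columns are. The documents do not support that: by randomized sequence, planned follow-up is equal and B shows no false difference. Early termination does not by itself change this, because a common cut-off varies follow-up between subjects without a systematic difference between arms. This stands, and it is why both readings are given. The two harms are alternatives and should not be added together.

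A reader might also infer that the sponsor dropped the ATE table. That is not shown. Protocol 8.1 planned separate SAPs for induction and ATE data, 8.8.2 left phase assignment to them, and parts of this SAP are redacted. All that can be said is that no ATE-only adverse event table is readable. Nor are crude percentages a departure: Protocol 8.8.2 uses them too.

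There are safeguards. Induction tables keep the randomized comparison, treatment duration is summarized for both periods (SAP 3.7.1), events are listed by subject, and adverse event rates are generally not tested. These reduce the harm. They do not supply ATE incidence by treatment: whole-study duration runs from first dose to last drug return without splitting placebo from 80 mg. Under sequence columns, subtracting Induction from overall counts yields only subjects whose first such event came later.

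**Conclusion.** The point holds in conditional form. The overall tables use percentages without person-time, over a window that crosses a treatment switch, and the protocol's ATE summary is not in the readable SAP. If columns follow treatment received, placebo versus active is confounded by a planned exposure ratio of 4.6 to 5.0; at 10% risk the spurious contrast ranges from 10.0/15.4/19.0% with 12 ATE weeks to 10.0/38.3/41.0% with 48. If columns follow the randomized sequence, there is no such contrast, but a hazard ratio of 2 is reduced to a ratio of percentages of 1.06.

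These sizes rest on an assumed 12-week risk, constant hazard and complete follow-up to the stated week; actual ATE durations are not given. An inference that the tables would manufacture a dose effect is not supported, since the planned 200 mg to 80 mg exposure ratio is only 1.09. The Induction results are untouched. This should be corrected, but it limits what the longer-term safety tables can show and does not undermine the controlled safety comparison.

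**What to change.** - Keep crude percentages for Induction, and state that it is the only placebo-controlled adverse event comparison.
- State the columns of the overall tables. Attribute each TEAE to the treatment being taken at onset, and divide time at risk at the ATE Day 1 dose.
- Add exposure-adjusted incidence rates per 100 patient-years with 95% confidence intervals, at least for TESAEs, adverse events of special interest and TEAEs leading to discontinuation.
- Restore the protocol's ATE summary by treatment received in the ATE, or record its removal and the reason in SAP 5.1.

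The cost is modest programming. First and last dose dates are already listed, and the ATE Day 1 dose date is already used to end the Induction window. The rates assume a roughly constant hazard, so they should stand beside the percentages, not replace them.
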